9 SAFETY EVALUATION

9.1 Adverse Events

9.1.1 Analysis Set

Analysis will be performed in SAF.

9.1.2 Analysis Items and Data Handling

1) Analysis Items

- (1) Overall adverse events, adverse drug reactions and number of deaths.
- (2) Classification of adverse events

2) Data Handling

An adverse event is any unfavorable or unintended sign (including an abnormal laboratory finding), symptom or disease during a clinical trial, whether or not related to the investigational product. Of note, tabulation will include adverse events whose symptoms have occurred/worsened during the period from the first dose of the study drug until 28 days after the discontinuation or Day 22 only if subjects will not join the ONO-4538-14 study (or until the start of subsequent anti-cancer therapy, whichever comes first). In addition, all adverse events that occur during the treatment period or the post-treatment follow-up period will be listed and reported.

All adverse events reported in this clinical study will be coded by SOC (System Organ Class) and PT (Preferred Term) using MedDRA (Current version). Treatment-emergent adverse events are those events that occur or worsen on or after the first dose of study treatment up until end of study treatment.

For the analysis of adverse events, only treatment-emergent adverse events (TEAEs) will be included in the summary tables.

In case the same adverse events in terms of SOC and PT occurs to one subject more than once, it will be considered as a single event, and the highest severity and relationship status among all events will be taken into account.

Severity of adverse events will be classified using NCI-CTCAE, and where NCI-CTCAE is inapplicable, it will be classified as grade 1 ('Mild'), grade 2 ('Moderate'), grade 3 ('Severe'), grade 4 ('Life-threatening or disabling') or grade 5 ('Death') based on the maximum intensity. With respect to the relationship to study drug, 'Related' will be regarded as related, and 'Not related' will be regarded as unrelated.

- (1) Number of deaths

The number of deaths will be defined as the total number of subjects who have died during the period from the first dose of the study drug until 28 days after the discontinuation or 22 days only if subjects will not join the 4538-14 study (or until the start of subsequent anti-cancer therapy, whichever comes first).

Select adverse events will be defined as adverse events to be coded as PTs in any of the categories specified in [Addendum 1 List of Select Adverse Events](#) (i.e., Endocrine Adverse Events, Hypersensitivity/Infusion Reactions, Gastrointestinal Adverse Events, Hepatic Adverse Events, Pulmonary Adverse Events, Renal Adverse Events and Skin Adverse Events).

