9.1.3 Analysis Methods

The analysis results will be summarized by dose level groups separately and totality.

1) Overall Adverse Events, Adverse Drug Reactions and Number of Deaths

- (1) The number of subjects (incidence rate) will be provided for all adverse events and adverse drug reactions. The data will be displayed as “subject number (incidence of subjects (%))”.
- (2) The numbers of deaths, subjects with Grade 3 or higher adverse events and adverse drug reactions, and serious adverse events and adverse drug reactions, and discontinuations due to adverse events and adverse drug reactions, and adverse events and adverse drug reactions led to death will be summarized.

2) Classification of Adverse Events

- (1) Adverse events will be summarized by SOC and PT. The data will be displayed as “subject number (incidence of subjects (%))”.
- (2) Incidences of adverse events and adverse drug reactions by SOC and PT will be summarized according to Grade. In addition, incidences of Grade 3 or higher adverse events and adverse drug reactions will be summarized by SOC and PT.
- (3) Incidences of adverse events and adverse drug reactions led to death will be summarized by SOC and PT.
- (4) Incidences of adverse events and adverse drug reactions leading to discontinuation of the study treatment will be summarized by SOC and PT.
- (5) Incidences of serious adverse events and adverse drug reactions will be summarized by SOC and PT.

(6) Incidences of select adverse events and adverse drug reactions will be summarized by categories and PT. In addition, incidences of select, Grade 3 or higher adverse events and adverse drug reactions will be summarized by categories and PT.

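### SAP 9.1.2 gives two end points for the same adverse event tables, and the supplied text does not reconcile them

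*SAP*

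**What the plan says.** The rules are all in SAP 9.1.2:

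- **Tabulation window.** Events that start or worsen from the first dose are tabulated "until 28 days after the discontinuation or Day 22 only if subjects will not join the ONO-4538-14 study", with a further cut-off: "until the start of subsequent anti-cancer therapy, whichever comes first".
- **Treatment-emergent events.** These are "those events that occur or worsen on or after the first dose of study treatment up until end of study treatment". For the analysis, "only treatment-emergent adverse events (TEAEs) will be included in the summary tables".
- **Listings.** Separately, "all adverse events that occur during the treatment period or the post-treatment follow-up period will be listed and reported".
- **Deaths.** Deaths are counted from the first dose "until 28 days after the discontinuation or 22 days only if subjects will not join the 4538-14 study", with the same anti-cancer therapy cut-off.

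SAP 9.1.3 builds the tables on these rules: overall, by grade, serious, select, fatal and discontinuation events. In the overall summary, the death count stands beside a row in which "adverse events and adverse drug reactions led to death will be summarized".

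On the design, SAP 3.4 gives one dose followed by three weeks of observation. SAP 4.3 separates a treatment period ending at Day 22 from a post-treatment follow-up period. SAP 3.3.2 sends completers who do not move to ONO-4538-14 into the Follow-Up phase.

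**The concern.** The first rule reaches into follow-up. The second stops at the end of study treatment, a point that the supplied text does not define. The second rule does not refer back to the first and does not repeat the anti-cancer therapy cut-off. Two programmers who each followed 9.1.2 faithfully could apply different date filters and produce different versions of every table in 9.1.3, including the select adverse event tables.

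Three things are at stake. Events starting in follow-up may be in or out of the reported incidences. The death count has its own window and may not match the fatal-event row printed beside it. The preliminary review of treatment-emergent events in SAP 12.3 and 12.4, which covered 18 subjects with data entered by 17 December 2014, rests on whichever window was used, and the SAP does not say which.

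**Working it through.** There is no plan figure to reproduce. The check sets the two rules side by side and counts days.

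**Inputs.** Single dose on Day 1 (SAP 3.4, Table 3). Treatment period to Day 22 (SAP 4.3, Table 3). Follow-up of 28 days (SAP 9.1.2, 4.3). Six subjects per group (SAP 3.7.1).

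**Step 1: where the rules agree and differ.** The first rule has two possible readings for a completer who does not join ONO-4538-14, because it can be parsed as 28 days after Day 22 or simply as Day 22.

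| End of study treatment means | First rule read as 28 days after Day 22 | First rule read as Day 22 |
|---|---|---|
| End of treatment period (Day 22 or discontinuation) | Non-joining completers lose Days 23 to 50; discontinuers lose up to 28 days | Completers agree; discontinuers lose up to 28 days |
| The whole tabulation window | Rules agree | Rules agree |

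So the rules agree for all subjects only if the end of study treatment is loose wording for the whole tabulation window, including the anti-cancer therapy cut-off.

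**Step 2: which reading the text favours.** Section 9.1.2 itself distinguishes the treatment period from the post-treatment follow-up period. In 9.1.3, one table covers events "leading to discontinuation of the study treatment will be summarized by SOC and PT", which treats study treatment as something with duration. Both point to Day 22 or discontinuation for the second rule. For the first rule, SAP 4.3 uses nearly the same wording to time a follow-up visit that is separate from the Day 22 visit, and SAP 3.3.2 sends non-joining completers on to follow-up. Both favour 28 days after Day 22, but neither section says so in study days.

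**Step 3: days removed from the tables, on the treatment-period reading.**

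- Non-joining completer, if the first rule means 28 days after Day 22: the window ends on Day 22 + 28 = Day 50. Post-dose days: 50 − 1 = 49. Days in the treatment period: 22 − 1 = 21. Removed: 49 − 21 = 28, and 28/49 = 57%.
- Discontinuer, taking Day 8 as an example: the window ends on Day 8 + 28 = Day 36. Post-dose days: 36 − 1 = 35. Removed: 28/35 = 80%.

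Both are maxima, because subsequent anti-cancer therapy can end the first window sooner.

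**Step 4: deaths.** Take a non-joining completer with a fatal event starting on Day 30 and death on Day 45. If the second rule ends at Day 22, the event is not tabulated. If the death window runs to Day 50, the death is counted. The count then has no matching fatal-event row. In a completer, both readings are needed.

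**Step 5: scale.** One subject in a group of six is 1/6 = 17 percentage points of incidence.

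**Step 6: roll-over subjects.** The Day 22 clause is worded for subjects who do not join. A cut-off for those who do can be inferred from the anti-cancer therapy clause, since SAP 3.5.1 counts immunotherapy as an anti-cancer product, but it is not stated.

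**The case against.** The best defence is that the two sentences should be read together. The tabulation window is the specific rule. If treatment-emergent events stopped at Day 22 or discontinuation, its follow-up part would have no effect on any table. Reading the end of study treatment as shorthand for that window gives both sentences work to do. The SAP calls the three weeks the treatment period, not study treatment, so equating the two is an inference. The reference to discontinuing study treatment also sits oddly in a one-dose study and is weak evidence of a defined end date.

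This is a plausible account of what was intended, and the fix below adopts it. It does not cure the text. The supplied documents never state the equivalence, and the same section treats follow-up as a period after treatment. A programmer who took the treatment-emergent sentence literally would not be misreading it.

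Other parts of the defence stand in full. Only the protocol synopsis was supplied, so a definition in the protocol body cannot be excluded. The trial has 18 subjects and performs no tests (SAP 10.2), and either version of the tables can be rebuilt from the data behind the listings.

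**Conclusion.** The inconsistency is real and should be corrected, but it is a reporting fault in a descriptive safety analysis. On the treatment-period reading, up to 28 days of onset time leave the tables for a subject who discontinues. The same holds for a non-joining completer if the first rule means 28 days after Day 22. The number of affected subjects is unknown, and the effect is zero if no event starts in follow-up. All events remain listed, and the pharmacokinetic objective is unaffected.

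A reader might infer more than the documents support:

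- **That a single dose makes treatment end on Day 1.** This would empty almost every table and does not fit a table of events leading to discontinuation of treatment.
- **That Day 50 is the stated window.** It is the better-supported parse for non-joining completers, but 9.1.2 never gives that day.
- **That deaths and fatal events will disagree.** In a completer this takes two contested readings together, since the death window carries the same ambiguity as the tabulation window.
- **That incidences will be understated by some known amount.** The documents give no event rates or onset pattern, so no such figure can be derived.

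**What to change.** In SAP 9.1.2, replace the end-of-study-treatment limit in the treatment-emergent definition with the tabulation window already used for adverse events and deaths, including the subsequent anti-cancer therapy cut-off. One window then governs treatment-emergent events, every adverse event table and the death count.

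Have the sponsor restate that window unambiguously in study days for three kinds of subject: those who discontinue, completers who do not join ONO-4538-14 (SAP 3.3.2 and 4.3 favour 28 days after Day 22, about Day 50), and those who roll over. The sponsor should confirm the completer and roll-over cut-offs, since neither is explicit now.

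Record which window the preliminary review in SAP 12.3 and 12.4 used, so that it is clear whether its figures match the final definition.

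The cost is a few sentences of SAP text and a change to the table filter. No new data are needed.

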9.1.3 Analysis Methods

The analysis results will be summarized by dose level groups separately and totality.

1) Overall Adverse Events, Adverse Drug Reactions and Number of Deaths

- (1) The number of subjects (incidence rate) will be provided for all adverse events and adverse drug reactions. The data will be displayed as “subject number (incidence of subjects (%))”.
- (2) The numbers of deaths, subjects with Grade 3 or higher adverse events and adverse drug reactions, and serious adverse events and adverse drug reactions, and discontinuations due to adverse events and adverse drug reactions, and adverse events and adverse drug reactions led to death will be summarized.

2) Classification of Adverse Events

- (1) Adverse events will be summarized by SOC and PT. The data will be displayed as “subject number (incidence of subjects (%))”.
- (2) Incidences of adverse events and adverse drug reactions by SOC and PT will be summarized according to Grade. In addition, incidences of Grade 3 or higher adverse events and adverse drug reactions will be summarized by SOC and PT.
- (3) Incidences of adverse events and adverse drug reactions led to death will be summarized by SOC and PT.
- (4) Incidences of adverse events and adverse drug reactions leading to discontinuation of the study treatment will be summarized by SOC and PT.
- (5) Incidences of serious adverse events and adverse drug reactions will be summarized by SOC and PT.

(6) Incidences of select adverse events and adverse drug reactions will be summarized by categories and PT. In addition, incidences of select, Grade 3 or higher adverse events and adverse drug reactions will be summarized by categories and PT.

9.2 Clinical Laboratory Evaluation

9.2.1 Analysis Set

Analysis will be performed in SAF.

9.2.2 Analysis Items and Data Handling

1) Analysis Items

(1) Hematology

Red blood cell count, mean corpuscular volume (MCV), mean corpuscular hemoglobin (MCH), mean corpuscular hemoglobin concentration (MCHC), hemoglobin, hematocrit, white blood cell count, differential white blood cell count (neutrophils, lymphocytes, eosinophils, basophils, and monocytes), and platelet count.

(2) Blood biochemistry

Albumin, alkaline phosphatase (ALP), aspartate aminotransferase (AST) (glutamic oxaloacetic transaminase [GOT]), alanine aminotransferase (ALT) (glutamic pyruvic transaminase [GPT]), total bilirubin, direct bilirubin, gamma-glutamyl transpeptidase (γ -GTP), total protein, creatinine, blood glucose, lactate dehydrogenase (LDH), blood urea nitrogen (BUN), uric acid, creatine kinase (CK) (creatinine phosphokinase [CPK]), phosphorus (P), calcium (Ca), sodium (Na), potassium (K), and chloride (Cl).

(3) Urinalysis (qualitative)

Specific gravity, protein, glucose, occult blood, and sediment (white blood cells and red blood cells).

2) Data Handling

Data will be analyzed as observed without imputing missing data.

Any laboratory values that fall below the detection or quantification limit will be imputed to be the detection or quantification limit.

9.2.3 Analysis Methods

The analysis results will be summarized by dose level groups separately and totality.

- 1) For laboratory values as continuous quantities, summary statistics (no. of subjects, mean, standard deviation, median, minimum, and maximum) will be provided for each laboratory parameter by the time of measurement, and frequency distribution will be created for laboratory values on ordinal scale parameters.

9.3 Immunologic Test

9.3.1 Analysis Set

Analysis will be performed in SAF.

9.3.2 Analysis Items and Data Handling

1) Analysis Items

Rheumatoid factor (RA), C-reactive protein (CRP), antinuclear antibody (ANA), SP-D, and KL-6.

2) Data Handling

Data will be analyzed as observed without imputing missing data.

Any immunologic test values that fall below the detection or quantification limit will be imputed to be the detection or quantification limit.

9.3.3 Analysis Methods

The analysis results will be summarized by dose level groups separately and totality.

- 1) Summary statistics (no. of subjects, mean, standard deviation, median, minimum, and maximum) will be provided for immunologic test values as continuous quantities, while frequency distribution will be created for those on an ordinal scale.

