3.3.3 Follow-up Phase

Those subjects receiving the investigational product who satisfy any of the Criteria for Entering the Follow-Up phase will proceed to the Follow-Up phase.

Table 3 Study schedule

Category	Study day	Screening Phase	Treatment Phase									Follow-Up phase	
			1			2	3	4	8	15	22		
			Before administration	After the start of the administration	After the end of the administration	1 hr	2 hr	8 hr					
Allowable range (days)	-7 to -1					-			±2	±3		+3	±7
Written informed consent		○ ¹											
Inclusion/exclusion criteria		○											
Virus tests		○ ²											
ONO-4538 administration			○										
Demographics		○											
Pregnancy test ³		○										○	○
Vital signs/weight		○	○ ⁴	○ ⁴	○ ⁴	○ ⁴	○ ⁴	○ ⁴	○ ⁴	○ ⁴	○ ⁴	○	○
/percutaneous oxygen saturation													
Performance Status		○										○	○
Chest X-ray ⁵		○										○	○
12-lead ECG		○	○	○	○	○	○	○	○	○	○	○	○
Hematology tests/urinalysis		○										○	○
/blood biochemistry tests												○	○
Immunology/hormone tests		○ ⁶										○	○
Serum drug concentration ⁷			○	○	○	○	○	○	○	○	○	○	○
Anti-ONO-4538 antibody			○									○	○
													●
Diagnostic imaging (e.g., CT, MRI) ⁹		○ ²											
Tumor marker ¹⁰							●						
Concomitant drugs/adverse events				←									→

○:essential, ●:optional

1. Begin administering the investigational product within 30 days of informed consent.
2. The data from virus tests performed within 1 year of enrollment, diagnostic imaging (e.g., CT, MRI) performed within 14 days of enrollment will be included.
3. Women of childbearing potential will undergo a serum pregnancy test in the screening phase and subsequently undergo urine pregnancy testing.
4. Other than weight.
5. Also perform at unscheduled visits as necessary if, during the study (from the time of informed consent to the end of the subjects' schedule), signs, subjective and objective symptoms, or test findings suggest respiratory disease.
6. SP-D and KL-6 will be measured in the screening phase and, as necessary, in the treatment phase.
7. Collect blood sample at 24, 48 and 72 hours after the completion of the administration on 2nd, 3rd and 4th day, respectively.
[REDACTED]
9. Check for brain metastases with head CT/MRI. Check for bone metastases with X-ray imaging, FDG-PET, or bone scintigraphy as required by the clinical symptoms.
10. Perform tumor marker assessment according to the cancer type of patient when required at Investigator's discretion.

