9.4.3 Analysis Methods

The analysis results will be summarized by dose level groups separately and totality.

- 1) Summary statistics (no. of subjects, mean, standard deviation, median, minimum, and maximum) will be provided for each Hormonal test parameter by the time of measurement.

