9.5.3 Analysis Methods

The analysis results will be summarized by dose level groups separately and totality.

Summary statistics (no. of subjects, mean, standard deviation, median, minimum, and maximum) will be provided for each vital sign parameter by the time of measurement.

9.6 12-lead ECG

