9.6.3 Analysis Methods

The analysis results will be summarized by dose level groups separately and totality.

- 1) For 12-lead ECG parameters (observed values of RR interval, QT interval, Fridericia's corrected QT interval [QTcF], QRS complex, and PR interval, and their changes [ΔQTcF , ΔQRS , and ΔPR]), observed value (HR) and change (ΔHR) of heart rate, summary statistics and frequency distribution for each category will be summarized at each time point.
- 2) For maximum QTcF, maximum ΔQTcF , maximum QRS, maximum PR, and maximum heart rate of subjects, frequency distribution for each category will be calculated.

Item	Classification
RR (ms) (observed value)	≤ 600 , > 600 – 1200 , > 1200
P-R (ms) (observed value)	≤ 120 , > 120 – 200 , > 200
QRS (ms) (observed value)	≤ 60 , > 60 – 109 , > 109
Heart rate (observed value)	≤ 50 , > 50 – 100 , > 100
QT interval, ΔQTcF (ms) (observed value)	≤ 450 , > 450 – 480 > 480 – 500 , > 500
ΔQTcF (ms) (change)	≤ 30 , > 30 – 60 , > 60

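### SAP 9.3.3 names no time point for the immunology summary and, as in the other laboratory sections, no change or shift is planned, so the summary cannot separate new ANA or RF positivity from positivity at entry

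*SAP*

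**What the plan says.** SAP 9.3.2 lists the immunology items: "Rheumatoid factor (RA), C-reactive protein (CRP), antinuclear antibody (ANA), SP-D, and KL-6" (RA is the SAP's abbreviation for rheumatoid factor, RF below). SAP 9.3.3 reports them by dose group and in total. Summary statistics (number of subjects, mean, SD, median, minimum, maximum) "will be provided for immunologic test values as continuous quantities, while frequency distribution will be created for those on an ordinal scale". The section mentions no visit, change from baseline or shift.

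The neighbouring sections do name a time point:

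- SAP 9.2.3 (haematology, biochemistry, urinalysis): statistics "will be provided for each laboratory parameter by the time of measurement".
- SAP 9.4.3 (hormones): statistics "will be provided for each Hormonal test parameter by the time of measurement".
- SAP 9.5.3 (vital signs): statistics "will be provided for each vital sign parameter by the time of measurement".
- SAP 9.6.3 (ECG), for observed values and changes: "summary statistics and frequency distribution for each category will be summarized at each time point".

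In SAP Table 3, immunology and hormone tests share one row, marked at screening and at later visits. Footnote 6 makes an exception for two markers: "SP-D and KL-6 will be measured in the screening phase and, as necessary, in the treatment phase".

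**The concern.** ONO-4538 is an antibody to PD-1, and SAP 3.2.3 excludes active autoimmune disease and a history of chronic or recurring autoimmune disease. The listed criteria do not name ANA or RF positivity itself, so a subject may be positive at entry. The useful safety result is what changes within a subject after dosing.

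There are two gaps. First, without a time point, a programmer following 9.3.3 literally could produce one mean or one frequency table per dose group that combines screening and post-dose values. Second, even with the time point restored, separate frequencies at each visit give only marginal counts. They do not show whether the subjects positive after dosing were already positive at entry.

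**Working it through.** **Step 1. Compare the summary sections.**

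| SAP section | Tests | Time point named | Within-subject change or shift |
|---|---|---|---|
| 9.2.3 | Haematology, biochemistry, urinalysis | Yes, in the clause on continuous values | None |
| 9.3.3 | RF, CRP, ANA, SP-D, KL-6 | No | None |
| 9.4.3 | TSH, free T3, free T4 | Yes | None |
| 9.5.3 | Vital signs, weight, SpO2 | Yes | None |
| 9.6.3 | 12-lead ECG | Yes | Change planned |

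9.3.3 is the only one of the five without a time point. On within-subject comparison it is no different from 9.2.3, 9.4.3 and 9.5.3.

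**Step 2. Does another section supply the time point?** SAP 4.3 sets windows and chooses which value represents a time point. It does not say that tables are produced by time point.

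**Step 3. What could each kind of table show?** The plan gives no figure to reproduce, so the counts here are assumed. The only input from the documents is n = 6 per dose group (SAP 3.7.1). Let a subjects be positive before dosing and b at one post-dose visit, with all 6 measured at both. The number of new positives then lies between max(0, b − a) and min(b, n − a).

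| a | b | Combined table | By-visit tables | New positives | Share of the n − a negative at entry |
|---|---|---|---|---|---|
| 0 | 2 | 2/12 = 16.7% | 0/6, 2/6 | exactly 2 | 2/6 = 33.3% |
| 1 | 1 | 2/12 = 16.7% | 1/6, 1/6 | 0 to 1 | 0/5 to 1/5 = 0% to 20% |
| 1 | 2 | 3/12 = 25.0% | 1/6, 2/6 | 1 to 2 | 1/5 to 2/5 = 20% to 40% |
| 2 | 2 | 4/12 = 33.3% | 2/6, 2/6 | 0 to 2 | 0/4 to 2/4 = 0% to 50% |

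The first two rows give the same combined table, although one has two new positives and the other at most one. By-visit tables separate those two rows, but they fix the number of new positives only when nobody is positive at entry. A shift table gives the number directly.

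**Step 4. Continuous markers, if values were combined.**

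- CRP: suppose 6 pre-dose values have mean m and all 6 rise by d at one post-dose visit. The combined mean is (6m + 6(m + d))/12 = m + d/2, so half the shift is lost.
- SP-D or KL-6: suppose there are 6 screening values with mean m and a single later value m + d, taken because it was judged necessary. The combined mean is (6m + m + d)/7 = m + d/7.

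**The case against.** The strongest reply is that nothing in the SAP orders pooling. SAP 4.3 assigns examination data to time points, and 9.3.3 reports a number of subjects, which fits poorly with a table that counts a subject more than once. By-visit tables are the natural reading and the missing words look like a slip. This stands: a reader might infer from 9.3.3 that pre- and post-dose values are pooled, but the text supports only that it does not say.

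A reader might also infer that immunology is singled out for having no within-subject comparison. It is not; only ECG has one. For ordinal results the contrast on time point is weaker too. In 9.2.3 the statistics "will be provided for each laboratory parameter by the time of measurement, and frequency distribution will be created for laboratory values on ordinal scale parameters", so the qualifier is attached to the continuous values and is not repeated for the ordinal ones.

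A third inference would be that a conversion could not be seen at all. SAP 10.3 provides a format for displaying individual data, and SAP 9.1.2 counts an unfavourable or unintended abnormal laboratory finding as an adverse event and lists all such events. With 6 subjects per group these are plausible routes, but neither is assured. Section 10.3 sets decimals without committing to an immunology listing, and ANA is absent from its tables. Addendum 1 has laboratory terms for thyroid, liver and kidney, but none for these five markers.

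Two further limits stand. RF is displayed as an integer in IU/mL, and no positivity limit is given for RF or ANA, so new positivity is not yet a defined quantity. SP-D and KL-6 are taken after screening only as necessary, so a systematic pre/post comparison is not available for them. Finally, the objective is pharmacokinetic and no tests are performed, so a shift table is an improvement rather than a requirement.

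**Conclusion.** The point holds as a minor, inexpensive improvement. SAP 9.3.3 leaves open whether visits are tabulated separately, and the planned summary cannot separate new ANA or RF positivity from positivity at entry. The documents do not support saying that values will be pooled, or that conversions will go unseen in every output.

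The size is illustrative only: with 2 of 6 positive before and after dosing, new positives could be 0 to 2, or 0% to 50% of the 4 subjects negative at entry. That rests on assumed counts, one post-dose visit and complete data. The d/2 and d/7 results apply only if values are in fact combined. The column layout of Table 3 is not legible in the copy reviewed, so the post-dose visits are not named here. The data are descriptive, in 18 subjects, and no planned test is affected.

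**What to change.** In SAP 9.3.3:

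1. Add the time-of-measurement qualifier used in 9.2.3, 9.4.3 and 9.5.3, applying it to frequencies as well as to summary statistics.
2. For RF and CRP, summarise observed values and the change from the last pre-dose value. Do the same for SP-D and KL-6 only in subjects with a post-dose value, with n shown, because those samples are taken as necessary.
3. Add one shift table by dose group for ANA and RF: pre-dose category against highest post-dose category, limited to subjects with both values.
4. State the category limits before data lock, for example the testing laboratory's reference limit or titre steps.

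The cost is a small wording change, one extra small table and the need to settle the category limits. No new sampling is needed. SAP 4.3 already accepts laboratory results from within seven days before enrolment as the pre-administration value.
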